Well-designed randomized controlled clinical trials demonstrating the efficacy of short implant rehabilitations are lacking to date.

The clinical performance of short and long implants should be compared at the level of areas having a good and comparable bone quality, the same bone height (this assumes the installation of short implants in sites able to receive longer ones), and for the resolution of the same type of edentulism by means of an identical prosthetic solution.

A reliable option is represented by 5 implants positioned in the interforaminal region of edentulous mandibles having bone height sufficient to receive standard-length implants, supporting a fixed full-arch prosthesis. The anterior mandibular region is usually characterized by high bone quality. Furthermore, the above-mentioned type of full-arch implant-supported rehabilitation possesses the best evidence of long-term success (Ekelund et al. 2003; Bryant et al 2007), being historically the first one performed and, to date, the most predictable too.

Specific Aims and Hypotheses

The aim of the present study is to evaluate the efficacy of 6 mm short implants compared with 11 mm long implants in comparable anatomic, surgical (no need for bone augmentation procedures), and prosthetic (fixed full-arch mandibular prosthesis) conditions. In particular, the null hypothesis is that there is no difference in terms of marginal bone level change (MBLc) between short and longer implants from prosthetic installation to 5 years of follow-up.

Study design and general information

This study has been designed as a multicenter parallel-group randomized controlled clinical trial (RCT) with a 1:1 allocation ratio. Three italian centers will be involved to the study. It will be reported according to the

CONSORT statement (http://www.consort-statement.org/). The Declaration of Helsinki principles will be followed, and all patients will sign a written informed consent form. The research protocol has been approved by the ethical committee of the University of Campania "Luigi Vanvitelli" (Aut. N. 13/2010).

Primary and secondary outcomes

The primary outcome will be the radiographic MBLc expressed as the change of MBL from prosthetic installation to the follow-up.

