The secondary outcomes will include: (i) implant survival rate, (ii) prosthesis survival rate, (iii) biological or technical complications. Surviving implant or prosthesis will be considered those still in function at the follow-up. Biological complications included peri-implant mucositis, defined as a reversible inflammation of the soft tissues surrounding an implant in function with no loss of supporting bone, and peri-implantitis, defined as an inflammatory process affecting the tissues around an osseointegrated implant in function resulting in loss of supporting bone (Zitzmann & Berglundh 2008. Technical complications will be categorized in minor and major complications. The formers require only chair side repair and included screw loosening, and veneer material fracture. The latter require additional laboratory procedures and/or replacement components and included prosthesis or framework fracture, screw fracture, implant fracture, extended wear requiring veneer renewal.

Sample size calculation

Sample size calculation revealed that group sample sizes of 13 per group achieved 80% power to detect noninferiority using a two-sample, one-sided test. The margin of non-inferiority (δ), that is the threshold value judged as clinically relevant, was 1.0 mm. The true difference between the means was assumed to be 0.0. In consideration of the one-tail nature of the non-inferiority test, the significance level (alpha) was set at 0.025. The data were drawn from populations with standard deviations of 0.9 and 0.9. Such a value was based on the long-term marginal bone loss data from the population of mandibular edentulous patients rehabilitated with Toronto bridges supported by conventionally loaded inter-foraminal long implants (Ekelund, Lindquist, Carlsson, & Jemt, 2003). Fifteen patients per group will be recruited to compensate for possible drop-outs.

Patient enrollment

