Inclusion criteria will be age between 18 and 75 years, total mandibular edentulism for at least 8 months, sufficient amount of native bone (no previous bone augmentation procedures) in the inter-foraminal area to host 11 mm-long and 4 mm-wide implants with \geq 1 mm of bone at the buccal and lingual aspects and \geq 3 mm of inter-implant distance (determined by computed tomography), systemic health and compliance with good oral hygiene. Exclusion criteria will be any disease, medication or drug that could jeopardize healing, osseointegration or treatment outcome, severe bruxism or other parafunctional habits, and unrealistic aesthetic demands. Smoking habit will be registered as heavy smoker (\geq 10 sig./day), light smoker (<10 sig./day), nonsmoker or former smoker. Patient eligibility in terms of bone dimensions will be determined on computer tomography (CT) scans, with the aid of an implant planning software.

Preparing and planning phase

Eligible patients received a complete anamnestic and clinical examination; hopeless teeth will be extracted and remaining teeth will be periodontally and restoratively treated, if needed. A 15% cut-off for full-mouth plaque score and full-mouth bleeding score will be requested for dentate patients. The prosthetic project will be accurately planned on cast models mounted in an articulator. When possible, the previous denture will be used as a reference.

Randomization and allocation concealment

The randomization and the allocation concealment will be carried out using a computer-generated randomization list and sealed sequentially numbered opaque envelopes by a person not otherwise involved in the study. Envelopes will be consecutively opened at the leading center and communicated to the surgeon at the first surgery.

First surgical phase

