Implant positioning will be performed by expert clinicians, following the same shared surgical protocol. A computer-aided bone-supported pilot surgical guide will be used during implant placement. All patients will be treated under local anesthesia using mepivacaine or articaine with adrenaline 1:100,000. A full-arch crestal incision, with distal releasing incisions if needed, will be performed and full thickness flaps will be raised. The mental nerves will be visualized and isolated. Five parallel implant sites will be prepared by calibrated burs and five 4 mm-wide implants (OsseoSpeed TX, Astra Tech Implant System, Dentsply Sirona Implants, Mölndal, Sweden) will be installed anterior to the mental foramens following the outline described by the manufacturer. 6 mm-long implants and 11 mm-long implants in the test and control groups will be placed, respectively. A minimum of 3 mm of inter-implant distance and 1 mm of bone at the buccal and lingual aspects will be required, with no need for augmentation procedures (if augmentation will be required, the patient would have been excluded from the study). If needed, an osteoplasty of the alveolar ridge will be placed flash to the bone. At the end of the surgical procedure cover screws will be positioned and a careful adaption of the flaps by means of an accurate suture will be assured in order to obtain primary closure and full periosteal coverage.

Postoperative care

The patients will be instructed to rinse with a chlorhexidine 0.12% mouthwash twice a day for 2 weeks and to avoid using the denture. Liquid and semisolid food will be prescribed for the first postoperative week, after which the sutures will be removed. Two weeks after the surgery, the denture will be properly relined avoiding direct contact with the fixture until the second-stage surgery. Patients will be controlled at 4, 8, and 12 weeks.

Second surgical phase and prosthetic procedures

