Peri-apical radiographs will be taken with Rinn Universal Collimator (Dentsply RINN, York, PA, USA) to limit exposure levels and Rinn film holders (XPC Extension Cone Paralleling System, Dentsply RINN, York, PA, USA), for correct positioning. Film-holder's position will be noted down for each implant site to increase reproducibility. The MBL will be determined (ImageJ 1.48a, National Institutes of Health, Bethesda, MD, USA) as the distance between the top of the micro-thread implant region and the most coronal level of the boneto-implant contact, using inter-thread distance for calibration. All the radiographic measurements will be performed by an experienced examiner not otherwise involved in the study, who will be kept unaware of the implant length by duly masking the radiograms. Mesial and distal MBL will be measured at each fixture and the MBLc from the baseline will be calculated at each follow-up (negative values in case of bone loss). Mean values will be calculated at the implant, patient and group level.

Statistical analysis plan

Descriptive statistics (means, standard deviations) of continuous variables and relative frequencies of discrete variables will be computed for each group separately using a statistical software program. Data will be analysed by an examiner blinded to the experimental groups using the patient as the statistical unit unless differently specified. Intention-to-treat (ITT) analysis will be adopted. The Fisher exact test for discrete intergroup variables and the one-sided Mann-Whitney U-test for MBLc values will be applied, because of the nature of the data. For primary outcome, statistical significance will be set at the alpha level of 0.025 using a one-sided test, while for two-sided tests statistical significance will be set at the alpha level of 0.05.

References

Bryant SR, MacDonald-Jankowski D & Kim K. (2007) Does the type of implant prosthesis affect outcomes for the completely edentulous arch? International Journal of Oral and Maxillofacial Implants 22 Suppl, 117-39.

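### Does leaving centre out of the allocation list and the primary test weaken this three-centre trial?

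*Combined protocol and SAP*

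**What the plan says.** The section on study design calls the trial a "multicenter parallel-group randomized controlled clinical trial (RCT) with a 1:1 allocation ratio" and adds "Three italian centers will be involved to the study". Under the sample size heading, "group sample sizes of 13 per group achieved 80% power to detect noninferiority using a two-sample, one-sided test", with an SD of 0.9 mm in each arm, a true difference of zero and a one-sided alpha of 0.025. Of the margin it says "that is the threshold value judged as clinically relevant, was 1.0 mm". It then adds "Fifteen patients per group will be recruited to compensate for possible drop-outs".

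Under randomisation, an independent person prepares a computer-generated list and opaque, sequentially numbered envelopes, and "Envelopes will be consecutively opened at the leading center and communicated to the surgeon at the first surgery". Blocks, strata and centre-specific lists are neither described nor ruled out.

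The statistical analysis plan takes the patient as the unit and states that "the one-sided Mann-Whitney U-test for MBLc values will be applied, because of the nature of the data". Centre does not appear there.

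Other sections limit how far centres can differ. On surgery: "Implant positioning will be performed by expert clinicians, following the same shared surgical protocol". There is also a common pilot guide, one implant system, six-monthly recall, and a single examiner who reads the radiographs masked to implant length.

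**The concern.** Read literally, one sequence of envelopes serves three centres. With only 15 patients per arm, a centre could by chance receive mostly short or mostly long implants. If centres also differed in marginal bone level change (MBLc), for instance through operators, smoking or maintenance, part of the arm difference would reflect centre. An analysis without centre would leave that variation in the error term when the result is set against the 1.0 mm margin. Many statisticians would stratify a multicentre trial by centre and adjust for it, so the omission stands out. At stake would be avoidable imbalance and lost precision. Bias and an inflated type I error are not in question, since unstratified randomisation remains valid.

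**Working it through.** **The plan's own figure.** With SD 0.9, margin 1.0 and true difference 0 (sample size section), n per arm = 2 × 0.9² × (1.960 + 0.842)² / 1.0² = 1.62 × 7.85 = 12.7, so 13. Power at 13 per arm is 81% by this normal approximation and 77.6% by the noncentral t distribution. With 15 per arm the t-test has 83.6%.

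**How often imbalance occurs.** Centre sizes are not given, so three patterns are assumed, with a list fixed at 15/15 (hypergeometric enumeration).

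| Centre sizes | Any centre 70:30 or worse | Any centre with one arm only |
|---|---|---|
| 10/10/10 | 47% | 0.06% |
| 14/10/6 | 36% | 1.7% |
| 18/8/4 | 68% | 10% |

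The first column does not rise steadily as centres become more unequal. It largely reflects small whole numbers: in a centre of four, every 3:1 split counts. It does not measure harm to the estimate.

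**What imbalance does to the estimate.** Assume equal centres with means of -s, 0 and +s mm. The between-centre variance is Vb = (2/3)s², and the shift in the arm difference from imbalance has SD = √(Vb × (30/29) × (2/15)).

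- s = 0.3: Vb = 0.06 (7% of 0.81), shift SD 0.09 mm.
- s = 0.5: Vb = 0.167 (21% of 0.81), shift SD 0.15 mm.

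This shift is not added to the planned standard error, which is 0.9 × √(2/15) = 0.33 mm. At s = 0.5 the within-centre part of the squared standard error is (0.81 - 0.167) × 2/15 = 0.086. The imbalance part is 0.15² = 0.023. Their sum is 0.109, and its square root is 0.33 mm. The total SD of 0.9 mm already pays for the imbalance.

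**Power and type I error.** Simulated with 8,000 trials per cell, normal data, total SD 0.9, true difference 0, centres 10/10/10 and all 30 patients evaluable. The Mann-Whitney test is shifted by the margin; this is an assumption, because the analysis plan does not say how the test uses the margin.

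| Design and analysis | s = 0 | s = 0.3 | s = 0.5 |
|---|---|---|---|
| Unstratified, Mann-Whitney (as planned) | 80.0% | 80.7% | 80.0% |
| Unstratified, t-test | 83.7% | 84.2% | 83.4% |
| Unstratified, linear model with centre | 80.6% | 83.9% | 89.0% |
| Stratified, linear model with centre | 83.4% | 86.4% | 90.9% |
| Stratified, van Elteren | 79.6% | 82.6% | 88.0% |

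The planned test does not lose power as centres diverge. A separate simulation with 40,000 runs per cell gave 79% to 81% for centre shares of variance from 0 to 0.3. Type I error of the planned test was 0.022 to 0.025 across both sets of runs.

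Like for like, stratifying with a centre term gains -0.3, +2.2 and +7.5 points for the t-type analysis. For the rank tests it gains -0.4, +1.9 and +8.0. With 26 evaluable patients the t-type gains are -0.9, +3.8 and +8.4.

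**What stratifying would cost.** The surgeon sees the implant length and so knows every earlier allocation at the centre. Suppose the surgeon always guesses the arm that is behind. A block of 2m then yields m + (4^m / C(2m, m) - 1)/2 correct guesses: 1.5 of 2, or 2.83 of 4. If the two sizes are equally likely, that is (1.5 + 2.83)/6 = 72%. The guessing rule needs no knowledge of the block sizes, so hiding them does not defeat it. Under one common list, a surgeon who sees only the allocations of a ten-patient centre is right about 53% of the time. If all three centres' allocations were known, the figure would be (15 + (4^15 / C(30, 15) - 1)/2)/30 = 17.96/30 = 60%. The section on the first surgery also allows a patient to be excluded if augmentation proves necessary, so foreknowledge of the arm could matter.

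**The case for a change.** The strongest reply is that the power reserve is thin: 77.6% by the t distribution at 13 per arm. A shared protocol standardises technique, but it does not make patients, operators or hygiene equal across centres. The protocol itself wants short and long implants compared under like conditions, and separate envelope stacks cost almost nothing while enrolment is open. Central opening could be kept.

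Part of this stands. The documents do not say how the list was restricted, and a stratified list would be more efficient if centres differed strongly. The thin reserve, however, does not come from centre. With 26 evaluable patients the unstratified t-test has 77%, 76% and 77% power at the three spreads, so the shortfall is the same with no centre effect at all. The gain of 7 points or more needs centre means of -0.5 and +0.5 mm, a gap equal to the whole margin, despite common surgery, hardware and reading. Nor is stratification free, because small blocks within centres raise predictability in a trial whose surgeons cannot be blinded.

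Allocation may also be finished: ethics approval dates from 2010, the document from 2019, and enrolment status is not stated. Adding a centre term after an unstratified list changes power by about -3, 0 and +6 points. As a sensitivity analysis it would leave the primary conclusion as it is.

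**Conclusion.** The concern does not hold. One list across three centres with an unadjusted two-group test is a valid design. With all 30 patients evaluable it delivers about 80% power at every centre spread examined, matching the stated target, with one-sided type I error at or below 0.025. Stratifying with a centre term would gain about 0 points if centres do not differ, 2 to 3 points (about 4 with 26 evaluable) at -0.3/0/+0.3 mm, and 7 to 8 points at -0.5/0/+0.5 mm. Against that stands a rise in correct guesses of the next arm from about 53% to about 72% with blocks of two and four. That is a matter of preference between two sound options. The missing description of blocks or strata is a gap in detail and does not show that the list was badly made.

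The conclusion rests on assumed centre sizes and centre means, normal data, a total SD of 0.9 mm that includes centre variation, and a Mann-Whitney test shifted by the 1.0 mm margin. How the test is meant to use that margin is a separate question and does not depend on centre.

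### Does the lack of a rule for a lost fixture leave the primary bone-level outcome open to bias?

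*Combined protocol and SAP*

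**What the plan says.** Under Primary and secondary outcomes: "The primary outcome will be the radiographic MBLc expressed as the change of MBL from prosthetic installation to the follow-up". Specific Aims and Hypotheses sets the period as prosthetic installation to 5 years. Implant survival is a separate secondary outcome: "Surviving implant or prosthesis will be considered those still in function at the follow-up".

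Under Baseline and follow-up examinations, marginal bone level is a radiographic distance from a landmark on the implant to the highest point of bone contact. Then "Mesial and distal MBL will be measured at each fixture and the MBLc from the baseline will be calculated at each follow-up", and "Mean values will be calculated at the implant, patient and group level". Assessments fall at baseline and at 1, 3 and 5 years.

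The Statistical analysis plan works "using the patient as the statistical unit unless differently specified" and states "Intention-to-treat (ITT) analysis will be adopted". For the primary outcome, "the one-sided Mann-Whitney U-test for MBLc values will be applied", at one-sided alpha 0.025. The radiograph examiner is masked to implant length and the analyst is blinded to group.

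No section says what a fixture lost after baseline contributes to the patient's mean, or what happens when a patient has no measurable fixture.

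**The concern.** A lost fixture cannot be measured at later visits. An analyst could leave it out of the patient's mean, carry its last value forward, or assign it a poor score. The intention-to-treat statement settles which patients are analysed and in which arm, but not this. Two analysts could therefore obtain different patient values from the same radiographs.

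The likely default leaves the lost fixture out. If short implants were lost more often, and had lost more bone before failing, the short arm would look better than it was. In a non-inferiority trial that error favours the claim. Some loss is foreseeable: the Background section reports historically higher failure of short implants, although it also cites studies that found no difference.

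**Working it through.** **Inputs from the documents.** Margin 1.0 mm, SD 0.9 mm in each arm, true difference 0, one-sided alpha 0.025, 13 per arm needed and 15 recruited (Sample size calculation). Five implants per patient (First surgical phase), so 15 × 5 = 75 fixtures per arm, or 13 × 5 = 65.

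**The plan's own figure.** n = 2 × [0.9 × (1.960 + 0.842) / 1.0]² = 12.7, rounded up to 13. Normal-approximation power at 13 is 80.9%. The stated sample size reproduces.

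**Assumptions not in the documents.** Fixture-loss rates; a gap (how much worse bone change is at a lost fixture than at a retained one) of 1 to 4 mm; the SD of 0.9 mm applied to patient means; and the margin entering the Mann-Whitney test as a 1.0 mm shift.

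**Chance of any loss.** With independent losses, the chance of at least one in 75 is 1 − (1 − p)^75: 53%, 78% and 98% for p = 1%, 2% and 5%.

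**One patient.** With one of five fixtures lost, leaving it out or counting it differs by gap / 5, that is 0.2 to 0.8 mm.

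**One arm.** Each lost fixture moves the arm mean by gap / 75 = 0.013 to 0.053 mm at 15 per arm, or gap / 65 = 0.015 to 0.062 mm at 13.

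**The test.** If the target counts lost fixtures, a retained-fixture analysis hides

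h = (short loss × short gap) − (long loss × long gap).

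The exact one-sided Mann-Whitney test rejects at U ≥ 124 with 13 per arm (size 2.21%) and at U ≥ 161 with 15 (size 2.27%). Set short implants truly worse by exactly 1.0 mm counting lost fixtures. The simulated chance of declaring non-inferiority is then:

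| Short / long loss | Gap, mm | h, mm | 15 per arm | 13 per arm |
|---|---|---|---|---|
| 3% / 0% | 1 to 4 | 0.03 to 0.12 | 2.8 to 4.9% | 2.6 to 4.5% |
| 5% / 1% | 1 to 4 | 0.04 to 0.16 | 3.0 to 6.2% | 2.8 to 5.6% |
| 2% / 2% | equal in both arms | 0 | 2.1 to 2.3% | – |
| 1% / 5% | 1 to 4 | −0.04 to −0.16 | 0.7 to 1.8% | – |
| 3% / 3% | short 4, long 1 | 0.09 | about 4% | – |
| 3% / 3% | short 1, long 4 | −0.09 | about 1.2% | – |

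The last two rows show that equal loss removes the bias only if the gap is also equal in both arms.

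Reaching 5% needs h of about 0.124 mm at 15 per arm or 0.140 mm at 13. Three excess short losses, each 3 mm worse, give 3 × 3 / 75 = 0.12 mm or 3 × 3 / 65 = 0.14 mm.

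**Would an added analysis help?** Consider one that carries forward the last value and gives losses before year 1 a common score 3 mm below the average long fixture. Assume that half the gap shows at the last visit and that a third of losses precede year 1. At 3% / 0% and 15 per arm the range falls from 2.8–4.9% to 2.3–3.4%. The same common score can mislead the other way. At 1% / 5%, with lost fixtures no worse than the rest, error is 3.0%, or 4.2% if two thirds of losses precede year 1; retained fixtures alone give 2.1 to 2.4% when lost fixtures are typical. Requiring both analyses to succeed would cut power at 13 per arm from about 73% to 69–71%.

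**The case for a change.** The strongest case for a change is that the omission touches the primary outcome, is not covered by the intention-to-treat statement, and could be closed with one sentence and radiographs already scheduled. A patient's value can move by up to 0.8 mm under the assumed gaps, which is close to the SD and the margin. Fixing the convention in advance would make the result reproducible whatever the losses turn out to be.

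The omission stands, and so does the patient-level arithmetic. The step to a defect in the analysis does not. The plan asks for means of measured fixtures, and a lost fixture offers no measurement, so most analysts would compute the same number. The error rates above 2.5% arise only against a target that counts lost fixtures, which the plan never adopts. Against bone change at fixtures still in function, the test keeps its nominal level. Losses are not concealed either, because survival is reported by arm.

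One case is left open: a patient who loses all five fixtures has no bone value under any averaging rule. That patient has failed on implant survival and, with nothing left to carry the bridge, on prosthesis survival. The event would be plain in the report of a trial with 15 patients per arm.

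**Conclusion.** This is missing detail that analysts fill sensibly, so the plan need not change. The value is unspecified rather than undefined, except for a patient with no measurable fixture. No stated rule is shown to be wrong, and none of the alternatives is clearly better: an analysis that counts lost fixtures needs an arbitrary score, only partly removes the possible bias, and can add bias in the other direction.

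Measured against a target that counts lost fixtures, the effect is modest and can go either way. False non-inferiority runs from 0.7% to 6.2% at 15 per arm over the scenarios tabulated, against an exact size of 2.27%. About three excess short losses, each 3 mm worse, are needed to reach 5%, in a type of rehabilitation that the Background section describes as "being historically the first one performed and, to date, the most predictable too". Masked measurement and blinded analysis make it unlikely that the convention would be picked to favour an arm.

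All of this rests on assumed loss rates and gaps, on the planning SD of 0.9 mm, and on the margin entering the test as a shift. Many losses concentrated in one arm would call for caution in reading the bone-level result, and the survival outcome would show it.

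### The trial is sized for non-inferiority, but the only analysis planned is ITT, with no supportive check in patients who received the allocated implant length

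*Combined protocol and SAP*

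**What the plan says.** The Sample size calculation section states a non-inferiority design. It reports that "group sample sizes of 13 per group" "achieved 80% power to detect noninferiority using a two-sample, one-sided test". The margin, "that is the threshold value judged as clinically relevant, was 1.0 mm", goes with a standard deviation of 0.9 in each group and one-sided alpha 0.025. On the true effect: "The true difference between the means was assumed to be 0.0". Fifteen patients per group are to be recruited to allow for drop-outs.

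The Statistical analysis plan section says "Intention-to-treat (ITT) analysis will be adopted" and names a one-sided Mann-Whitney test at 0.025 for marginal bone level change (MBLc). It does not repeat the margin. No per-protocol, as-treated or sensitivity analysis is named anywhere, and no rule covers a patient who receives a length other than the one allocated, or one with no 5-year MBLc.

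Three other places bear on the point:

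- Specific Aims and Hypotheses is worded as a test of equality: "the null hypothesis is that there is no difference in terms of marginal bone level change (MBLc) between short and longer implants".
- Randomization and allocation concealment has the surgeon told the allocation at the first surgery.
- First surgical phase deals with sites that turn out to need augmentation: "if augmentation will be required, the patient would have been excluded from the study". It does not say whether this can happen after the envelope is opened, or whether such a patient stays in the ITT set.

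**The concern.** In a superiority trial, analysing patients as randomised is usually conservative, because mixing treatments across arms shrinks the observed difference. In a non-inferiority trial the same shrinkage helps the claim when the new treatment really is worse. An analysis by treatment received is therefore a useful second look, and this plan has none.

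The arms are small, so a single patient is 1/15, or 6.7%, of an arm. If the short implant lost bone faster by the full margin and one or two patients were switched, the chance of a false non-inferiority claim would exceed the nominal 2.5%. A reader of the results would have no pre-specified analysis showing whether the conclusion holds in patients treated as allocated.

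The augmentation exclusion raises a related question. If it can be applied after allocation is known, removing those patients conflicts with the ITT statement.

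**Working it through.** **Inputs.** From the Sample size calculation section: margin 1.0 mm, SD 0.9, true difference 0, one-sided alpha 0.025, power 80%, 13 per group needed, 15 recruited. Assumed, because the documents give no figure: 0 to 3 short-arm patients receive long implants in all five positions and are analysed as randomised.

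**1. The plan's own figure.** n per group = 2 × SD² × (z₀.₉₇₅ + z₀.₈₀)² / margin² = 2 × 0.81 × (1.960 + 0.842)² / 1.0² = 12.72, rounded up to 13. This reproduces the stated size. Power at 13 is 80.9% by the normal approximation and 77.6% by the noncentral t.

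**2. Dilution.** The false-claim rate is judged with the true deficit equal to the margin. If k of n short-arm patients have the long-arm mean, the expected ITT deficit is 1.0 × (1 − k/n) mm. By the normal approximation the false-claim rate is Φ[(k/n) / (0.9 × √(2/n)) − 1.96].

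For n = 15 the standard error is 0.9 × √(2/15) = 0.329. With k = 2 the deficit falls to 0.867 mm, and Φ(0.133/0.329 − 1.96) = Φ(−1.55) ≈ 6.0%.

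This approximation is somewhat high, because it ignores the extra spread that switched patients add to their arm and uses normal rather than t critical values. Simulation of the margin-shifted tests takes both into account (t-test 200,000 runs, exact Mann-Whitney 40,000 runs):

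| Full switches | Deficit, n = 15 (mm) | Normal approx., n = 15 | t-test, n = 15 | Mann-Whitney, n = 15 | t-test, n = 13 | Mann-Whitney, n = 13 |
|---|---|---|---|---|---|---|
| 0 | 1.000 | 2.5% | 2.5% | 2.4% | 2.5% | 2.1% |
| 1 | 0.933 | 3.95% | 3.6% | 3.2% | 3.6% | 3.2% |
| 2 | 0.867 | 6.0% | 5.1% | 4.5% | 5.3% | 4.7% |
| 3 | 0.800 | 8.8% | 7.1% | 6.1% | 7.5% | 6.3% |

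Repeat runs agreed to within about 0.3 percentage points. One switch in each direction at n = 15 also gives about 5% by t-test.

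**3. Partial switches.** The patient's value averages five implants. If one of the five is switched and each contributes equally, that patient's mean moves by 1.0/5 = 0.2 mm. With one or two such patients at n = 15 the false-claim rate is about 2.7% to 3.0%.

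**4. Other true effects.** With no true difference, t-test power at n = 13 is 77.3% with no switches and 77.4% with two, so there is no effect. If the short implant is better by 0.5 mm, two switches lower the chance of declaring non-inferiority from 98.3% to 97.0%.

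**5. The supportive set.** If switching is unrelated to outcome, the false-claim rate in patients treated as allocated stays at about 2.4% to 2.6% in every scenario above. Its t-test power is about 78% at 13 per group, 74% at 12 and 70% at 11.

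**The case against.** The strongest objection is that the triggering event is hypothetical. Treatment is one surgical placement of a fixed length, so there is no adherence to drift over five years. Every patient must have CT-confirmed bone able to take the 11 mm implant, so either length should fit. Placement is planned with software and guided by a template. The one intra-operative problem the protocol foresees, a need for augmentation, leads to exclusion and not to a change of length. This stands. It makes switching unlikely without ruling it out, and the figures above are conditional on it.

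A reader might infer that any departure from protocol favours the short implant. The documents and the arithmetic do not support that. The bias needs an actual mixing of 6 mm and 11 mm implants and a short implant that is truly worse. It vanishes at the plan's own assumption of zero difference and reverses if the short implant is better.

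A reader might also want success required in both sets, with the per-protocol set limited to patients with 5-year films. That goes too far. Selecting on films can remove early failures and withdrawals, which could hide the short arm's worst cases, and a joint requirement costs power. A supportive analysis is enough.

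**Conclusion.** The gap is real but modest. A trial sized for non-inferiority names only ITT and has no pre-specified check in patients treated as allocated. In the worst case for that omission (true deficit equal to the 1.0 mm margin, two full switches, 15 per arm), the false non-inferiority rate about doubles, from 2.5% to 5.1% by t-test or from 2.4% to 4.5% by Mann-Whitney. Partial switches do far less.

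It would be wrong to conclude that the error rate is already above 2.5%. With no switches it is at the nominal level, and the documents report none. The sample size is unaffected.

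Separately from any switching rate, the exclusion of patients found at surgery to need augmentation must be reconciled with the ITT statement.

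**What to change.** In the Statistical analysis plan section:

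1. Keep ITT as primary and define it as all randomised patients in the arm assigned. Reconcile this with the augmentation exclusion in First surgical phase: any patient excluded after the envelope is opened stays counted and reported in the ITT set. State how missing 5-year MBLc is handled.
2. State the decision rule: non-inferiority is claimed if the lower limit of the two-sided 95% confidence interval for short minus long (bone loss negative) in 5-year MBLc is above -1.0 mm.
3. Define a per-protocol set by receipt of the allocated implant length, not by availability of 5-year films. Pre-specify the same margin-based comparison in it as a supportive analysis.
4. State that a non-inferiority claim will be described as not robust if the two sets disagree, with both intervals shown.

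The cost is a few lines of text and one repeat analysis, with no new data and no more patients. The drawback is power: with 12 or 11 per group in the supportive set, t-test power is about 74% or 70%. A disagreement may therefore reflect a wider interval and not bias, and the report should say which it appears to be.
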